Participants will be eligible for the study if they report experiencing symptoms that would indicate a clinical diagnosis of an OUD within the past 12 months. This will be evaluated by the participant's responses provided on the Structured Clinical Interview for DSM-5 (SCID-5), a semi-structured interview guide for making the major DSM-5 diagnoses, including substance use disorders. Participants will be eligible for the RCT if they meet criteria for at least a mild severity OUD according to this measure. Participants will also be eligible for the RCT if they report taking buprenorphine as pills, tablets, or films (excluding injection and patch routes of administration) specifically for the treatment of an OUD. Participants previously engaged in buprenorphine treatment who report a lapse in medication usage of at least 30 consecutive days within the previous 6-months will be eligible for the study since we will consider the resuming of the medication a *new treatment episode*. In addition, participants must report taking at least one dose of prescribed buprenorphine within the 10 days prior to the enrollment assessment interview to be eligible for the trial. There are other instances in which buprenorphine may be prescribed such as the immediate management of opiate withdrawal symptoms (as is usually seen in detoxification centers). For this study, since retention on buprenorphine treatment is the primary outcome of interest, participants will not be eligible for the study if they are only receiving buprenorphine for detox and do not plan to continue the treatment past the opiate withdrawal phase. In addition, participants will not be eligible for the study for similar reasons if they are prescribed longer-acting

forms of buprenorphine such as the injectable form or patch form, as these administration methods do not follow similar retention metrics as the pills, tablets, or films.

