Following the consent process, participants will complete the baseline assessment (*“Baseline, Enrollment, Randomization”*). The baseline assessment will take approximately 2 hours to complete and participants will be remunerated up to \$60 for their participation (\$50 for baseline assessment + \$10 for voluntary urine sample). Because we will need to contact participants for follow-up assessments, the research staff member will collect detailed contact information using the Locator Form during this assessment. This information will include the participant’s phone number(s), address(es), e-mail address(es) and contact information for family members/friends who would know how to reach them. Participants will be asked to complete a survey during the enrollment assessment either with a research staff member (via researcher / study therapist administered interviews in-person or by phone or video chat) or use self-report surveys (completed electronically via tablet or emailed survey link or in a paper version if preferred by the participant) to gather data to assess additional demographics, pain and functioning, substance use, and use of buprenorphine. The baseline assessment will also include a researcher administered interview, delivered in-person, by phone, or video chat, containing the Time Line Follow Back (TLFB) assessment, which is designed to assess for opioid and other substance use over a given time period. Information regarding buprenorphine treatment and recent medication usage will also be collected via the TLFB and will be used to confirm study eligibility. In addition, participants will be given a researcher administered diagnostic interview (Structured Clinical Interview for DSM-5; SCID-5), delivered in-person, by phone, or video chat to confirm the presence and severity of an Opioid Use Disorder (OUD) diagnosis within

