9.2 Sample Size and Randomization

Sample size estimates were guided by our prior work on psychosocial interventions for pain during addiction treatment and prior trials that used MAT retention as an outcome and calculated using Stata. In studies of buprenorphine programs, retention varies widely but generally is around 50% in studies with at least 3-months of follow-up and robust sampling.²⁶ For a time-to-event analysis we assumed an event rate of 50% in EUC, where the event is dropping out of treatment, and based calculations on a two-sided $\alpha=0.05$. A hazard ratio of 0.5 (i.e., PPMI less likely to drop out of treatment) would achieve >85% power with a sample size of 200, or 100 per group. Given that we will be able to infer treatment retention even for participants who drop out of the study, our primary outcome analysis was based around our complete sample size of 200.

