The primary outcome measure for this study is retention on buprenorphine treatment as measured over 3-months. Secondary Aim 1 for this study is retention on buprenorphine treatment over 12-months. This will be operationalized as time to first episode of buprenorphine treatment non-adherence. Non-adherence, or discontinuation of treatment, will be defined as a consecutive period of 7 or more calendar days without taking buprenorphine. Buprenorphine retention will be collected in a variety of ways for this study:

- (1) as part of the TLFB assessment, which will be administered at the baseline enrollment assessment and the 1-, 3-, 6-, 9-, 12-month follow-ups in which the participant will be asked to recall on which days they took their buprenorphine medications;
- (2) as part of weekly surveys completed during the study;
- (3) through medical record reviews at the treatment sites (as applicable when participants and clinics have provided proper releases of information) to review urine toxicology screens and/or prescription fill records;
- (4) through urine analysis at 1-, 3-, 6-, 9-, and 12-month follow-up

Medical Records will be reviewed, when applicable, for the following piece of information regarding buprenorphine treatment: (1) number treatment appointments scheduled with the buprenorphine provider, (2) number of treatment appointments completed with the buprenorphine provider, (3) number of treatment appointments scheduled but not completed by the participants with the buprenorphine provider, (4) urine toxicology results obtained as part of buprenorphine treatment only, (5) prescription fills for buprenorphine prescriptions through the VA pharmacy. The research team has extensive experience obtaining prescription fills and other data through CPRS from prior studies.

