We will first descriptively calculate the percent still receiving buprenorphine at the 1- and 3-month follow-ups. The independent variable of interest is an indicator of group (PPMI vs.

EUC). Analysis will use an intent-to-treat framework, where participants are classified by the condition they were randomized to, regardless of what they received. Cox Proportional Hazards regression models will be used to test the association between group assignment and time to dropping out of buprenorphine treatment at 3-months. We will test if assumptions for this modeling technique are met, and if they are not, consider including a covariate*time interaction or stratification in Cox modeling, or variable transformations or alternative modeling strategies, if necessary.

The secondary aims are:

Secondary Aim 1: Conduct a randomized controlled trial (RCT) comparing remotely delivered PPMI (n=100) to EUC (n=100) to assess the impact of randomization to PPMI on retention on buprenorphine treatment over 12-months.

Secondary Aim 2: Determine the impact of remotely delivered PPMI on pain level, pain-related functioning, and frequency of substance use over 3-months.

Secondary Aim 3: Determine the impact of remotely delivered PPMI on pain level, pain-related functioning, and frequency of substance use over 12-months.

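### The 3- and 12-month Cox models for retention name no baseline covariate, although baseline buprenorphine-taking is already recorded; adjusting for it would be a nearly free gain in efficiency

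*Combined protocol and SAP*

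**What the plan says.** Section 9.6 gives the primary analysis: "Cox Proportional Hazards regression models will be used to test the association between group assignment and time to dropping out of buprenorphine treatment at 3-months". The group indicator is the only model term named, there and in the 12-month model for Secondary Aim 1. Section 9.3 describes the same Cox analysis and adds no covariate. In 9.6, a covariate-by-time term or stratification appears only as a remedy if the model assumptions fail.

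Section 9.5.1 defines the event as the first run of 7 or more consecutive days without buprenorphine and makes the TLFB the main outcome measure. The same section schedules the TLFB at baseline and at every follow-up, as an interview "in which the participant will be asked to recall on which days they took their buprenorphine medications". Section 6.2.2 confirms that the baseline interview covers this: "Information regarding buprenorphine treatment and recent medication usage will also be collected via the TLFB and will be used to confirm study eligibility". Randomisation follows completion of all baseline data collection (6.2.2, Randomization).

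Entry leaves baseline taking free to vary. Section 4.1 requires that "participants must report taking at least one dose of prescribed buprenorphine within the 10 days prior to the enrollment assessment interview", and it also admits people who have resumed after a lapse of at least 30 consecutive days.

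Two other passages bear on adjustment. For the secondary mixed models of pain and function, 9.6 includes the baseline value of the response among the independent variables. Section 5.1 (Treatment as Usual) says that treatment-experience data will be gathered at baseline and follow-up so that confounding can be controlled, but it lists no variables and names no model.

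**The concern.** In a Cox model, leaving out a variable that predicts the event pulls the estimated treatment hazard ratio toward 1 and costs power, even when randomisation has balanced the variable. Days missed shortly before enrolment are a plausible predictor of a later 7-day gap. They measure the same behaviour on the same instrument, and a daily taker and a person who took one dose in the last 10 days can both enter. The randomisation strata do not capture this: two people with the same sex, heroin history and veteran status can differ widely on it.

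The plan adjusts the pain and function models for baseline but leaves its single primary outcome unadjusted. About 79 events are expected and the assumed effect is large, so there is little slack if the true effect is smaller. Fixing the covariate in advance also fits the commitment in section 9.1 to plan the main analyses a priori.

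**Working it through.** **Inputs from section 9.2.** Two-sided 5% level; hazard ratio 0.5; full sample of 200. On the control rate: "For a time-to-event analysis we assumed an event rate of 50% in EUC". On power: the design "would achieve >85% power with a sample size of 200, or 100 per group". I take the 50% as cumulative at 3 months.

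**Reproducing the plan's figure without adjustment.**
- PPMI event rate under proportional hazards: 1 − 0.5^0.5 = 29.3%.
- Expected events: 100 × (0.500 + 0.293) = 79.3.
- Schoenfeld: power = Φ(√79.3 × |ln 0.5| / 2 − 1.96) = Φ(3.086 − 1.960) = Φ(1.126) = 87.0%.
- Freedman: Φ(√79.3 × 0.5/1.5 − 1.96) = Φ(2.968 − 1.960) = Φ(1.008) = 84.3%.
- Schoenfeld with 50% events in both arms (100 events): 93.4%.

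The stated figure stands on Schoenfeld's formula with no covariate. With 87% as the starting point, no adjustment could add more than 13 points.

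**What adjustment could add.** The documents give no association between baseline taking and discontinuation, so its strength is an assumption, shown as a range. The simulated hazard is λ·exp(γx + A·ln HRc), where x is a standard normal covariate, A is the PPMI indicator and exp(γ) is the hazard ratio per SD. λ is set so that 50% of EUC have the event by 3 months. HRc, the hazard ratio given the covariate, is set so that 3-month event-free survival in PPMI is 0.5^0.5 = 0.707; the unadjusted (marginal) hazard ratio is then about 0.5. There are 100 per arm, censoring at 3 months, and Wald tests of group with and without x. Each setting had 4,000 to 5,000 runs (Monte Carlo error about 0.5 point).

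| HR per SD | HRc | Power, group only | Power, adjusted | Gain (points) |
|---|---|---|---|---|
| 1.2 | 0.497 | 85.6% | 86.2% | 0.5 |
| 1.35 | 0.492 | 85.7% | 87.4% | 1.7 |
| 1.5 | 0.486 | 87.6% | 89.2% | 1.7 |
| 1.75 | 0.472 | 86.0% | 90.2% | 4.3 |
| 2.0 | 0.458 | 86.4% | 92.2% | 5.8 |
| 2.5 | 0.429 | 86.6% | 95.4% | 8.9 |

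Gains were computed before rounding.

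**Sensitivity to the assumptions.**
- *Binary covariate.* If poor baseline taking affects 20 to 30% of participants, the gain is at most 0.5 points at a hazard ratio of 1.5, 1.3 to 1.8 at 2, 3.6 to 4.4 at 3, and 5.7 to 7.1 at 4.
- *Hazard ratio 0.5 read as conditional on the covariate.* Group-only power then falls below the design figure. Omission costs 0.5 points at 1.2 per SD, 2.5 at 1.5 (83.8% against 86.2%), 5.9 at 1.75 (80.4% against 86.4%) and 8.4 at 2.0 (78.4% against 86.8%).
- *Smaller true effect.* At a marginal hazard ratio of 0.6 there are 84.0 expected events and group-only power is 64.9% by Schoenfeld. Adjustment adds 0.7 points at 1.2 per SD, 2.9 at 1.5, 6.7 at 1.75 and 10.3 at 2.0.

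All of these figures are for the 3-month analysis; the 12-month model was not simulated.

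**The case against.** The strongest reply is that nothing here is wrong. A group-only Cox model is a valid intention-to-treat test, and the sample size never relied on adjustment. Both statements stand.

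A second reply is that silence is not exclusion. Section 9.6 mentions covariates as a remedy for failed assumptions, and section 5.1 speaks of controlling for confounding. It would also overread section 6.2.2 to say that the baseline TLFB serves eligibility only: that section does not say so, and 9.5.1 lists the baseline interview among the sources of retention data. This stands too, but neither passage fixes a covariate for the primary model in advance.

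A third reply is that the documents themselves support other covariates better. Section 4.3 says that retention trajectories differ by sex and by heroin history, and these strata are also absent from the Cox models. That is a fair reason to include them as well, not a reason to leave baseline taking out.

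Finally, the proposed variable is uneven, because someone who started recently has a shorter look-back. A percentage of available days handles this only in part.

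A reader might infer that baseline taking is the baseline value of the outcome, so that its absence is the same omission as dropping baseline pain from a pain model. It is not: a time to a first 7-day gap after enrolment has no baseline value. Prior taking is a related and plausibly prognostic variable.

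**Conclusion.** The point holds as missed efficiency. Both Cox models omit a baseline measure of the same behaviour that is collected before randomisation. With an unadjusted hazard ratio of 0.5, the likely gain from using it runs from about 0.5 to 9 points of power across assumed hazard ratios per SD of 1.2 to 2.5. At weak to moderate strength (1.2 to 1.5) it is about 0.5 to 2 points, and at 1.75 to 2.0 about 4 to 6. The size rests wholly on that assumed strength, on exponential times and on a normal covariate.

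A reader might infer that the trial is underpowered, or that it loses 5 to 10 points by this omission. The documents support neither. The power above 85% reproduces unadjusted. Gains of that size need a strong covariate, and power falls below the design figure only if the hazard ratio of 0.5 is taken as conditional on a variable that section 9.2 never mentions. The change is worth making because it costs almost nothing and would help most if the true effect is smaller than planned.

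**What to change.** In section 9.6, for Primary Aim 1 and Secondary Aim 1, state that each Cox model will include, besides group, the percentage of days on which buprenorphine was not taken in the 30 days before enrolment (or since the start of the current treatment episode, if shorter), from the baseline TLFB. Fix how it enters the model before any outcome is examined by arm; a continuous linear term is the simplest choice. Report the group-only model as a sensitivity analysis. The randomisation strata (sex, past-year heroin use, veteran status) can go into the same models as main effects. That makes five terms in all, or 79.3 / 5 = about 16 expected events per term at 3 months.

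The cost is a short addition to the plan and no new data. The baseline covariate uses one degree of freedom, and the three strata would use three more. The reported hazard ratio becomes conditional on the covariates and will tend to lie further from 1 than the unadjusted one: in the table above, 0.458 corresponds to a marginal 0.5 at 2.0 per SD. Reporting both models lets readers see the difference.

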In practice, we anticipate that we will need to screen about 800 individuals (goal of 200 randomized/50% eligibility rate based on pain/90% eligibility rate based on OUD diagnosis/70%eligibility rate of new buprenorphine induction/80% consent rate). We estimate that 80% (n= 160) will provide follow-up data for self-reported outcomes. This is based on our prior work in addiction treatment patients utilizing various retention strategies tailored specifically to this population. It is worth noting that we will calculate our primary outcome (treatment adherence) conservatively and may assume that lost to follow-up is non-adherent. Thus, we will have follow-up data on 100% of those randomized for our primary outcome. We anticipate the following racial and ethnic composition of the sample: approximately 74% White, 18% Black, 3% American Indian/Alaska

Native, 3% Asian, and 1% Native Hawaiian or Other Pacific Islander. Approximately 7% of the sample for this study is estimated to be of Hispanic ethnicity. We anticipate that approximately 41% of the sample will be female in the community population and 10% of the veteran sample will be female. Regarding female participants specifically, we estimate that of the community sample, approximately 76% will be White, 20% will be Black, 2% American Indian/Alaska Native, and 2% Asian. Approximately 7% of the female sample will be of Hispanic ethnicity. We estimate that of the female veteran sample, approximately 60% will be white, 20% will be Black, 10% will be American Indian/Alaskan Native, 10% will be Asian. Approximately 10% of the sample will be Hispanic. Figure 2 below describes the recruitment and enrollment flow expected for participants into this study. To ensure the rigorous conduct of this study, we will utilize the CONSORT checklist and flow diagram to document participant accrual, flow and retention at all stages of the study across all recruitment locations.

Figure 2: Study Flow Diagram for Persist Study RCT

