Once a participant has provided informed consent, they may begin the baseline assessment with the research administered interview to confirm eligibility (e.g. the presence of an OUD diagnosis of at least mild severity within the past 12 months as measured by the Structured Clinical Interview for DSM-5). Participants will not be considered enrolled in the trial until full eligibility has been confirmed. Those who do not meet criteria for a diagnosis of an OUD of at least a mild severity within the past 12 months will be notified they are not eligible for the RCT, thanked for their time, and receive study payment for the assessment. Eligible participants will continue and complete the remaining parts of the baseline assessment, be considered enrolled into the trial, and will be eligible for randomization. Following the completion of all baseline study activities, participants will be randomly assigned to either the PPMI or EUC conditions. Stratified random assignment to intervention (PPMI) and control (EUC) conditions will be employed by gender (operationalized as biological sex assigned at birth), past year use of heroin (yes/no), and veteran status (community/veteran). While utilizing multiple randomization blocks can complicate the enrollment process, there is evidence that the trajectories of treatment retention and outcomes varies between men and women, as well as between those with history of heroin use versus those without heroin use. The project biostatistician will guide the randomization process. To prevent the possibility that staff could unwittingly manipulate patient assignment to treatment, a computerized randomization technique will be used, wherein the odds of treatment assignment change, based on the immediately preceding assignments, but odds are not truly fixed, as in strict balancing. Sequential runs of assignment to one condition are possible but are equalized by the end of a randomization block of participants. Randomization to conditions will be monitored by the Project Managers in conjunction with the project PIs and biostatistician to ensure that conditions remain balanced and will revisit the blocking procedures should any imbalances occur during the trial.

Secondary Aim 4: Enrollment of participants and providers for qualitative interviews

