Both the PPMI and EUC conditions will be overlaid onto an episode of OUD treatment with buprenorphine at an outpatient clinic. While we will be recruiting from multiple predetermined recruitment sites (listed above in Section 4. "Selection and Enrollment of Participants"), we will also be recruiting from the community through posted flyers, newsletters, social media/online platforms, and the project website. We may not be aware of the specific treatment requirements or programming at all locations that potential participants may be receiving their buprenorphine treatment. Due to the varied nature of buprenorphine treatment at outpatient substance use clinics, it is unlikely that participants across sites will receive the same treatment experience. However, since all participants will currently be receiving buprenorphine for the treatment of an OUD through a provider's prescription, we assume that participants will all be receiving the minimal standard of care dictated in the buprenorphine prescription guidelines (e.g. regularly meeting with their prescribing physician in order to renew their prescription). The level of participant involvement with their buprenorphine provider (e.g. frequency of appointments, requirements for outside counseling in addition to buprenorphine treatment, requirements for providing drug screens, etc.) may vary from clinic to clinic, as will exposure to other forms of substance use treatment (e.g. relapse prevention) and/or 12-step principles to encourage abstinence and improve coping skills. We will

ask participants to provide information regarding treatment experiences during the baseline (enrollment) interview and at all follow-up assessments in order to control for any potential confounding factors during analyses. No efforts will be made to influence the prescribing practices of other providers and study therapists will be barred from discussing clinical information about participants with any treatment providers, except in cases in which reporting (ex. suicide, homicide, child abuse) is clinically necessary.

Information/data sharing with the participant's provider

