9.2.1 Treatment Assignment Procedures

Details regarding how participants will randomly be assigned to one of the two study conditions (PPMI vs. EUC) are described above (see Section 5. “Study Conditions”, Section 6.2.2 “Enrollment, Baseline, and Randomization”, and Section 6.2.3 “Blinding”).

Randomization will be stratified by gender (biologically assigned male versus biologically assigned female at birth), past year use of heroin (yes/no), and veteran status (community/veteran). There is no sample size goal for each stratum, although strata assignment

and condition assignment will be monitored throughout the study to ensure an imbalance does not occur that could impact the ability to report on main study outcomes. Data on adherence to the intervention condition's protocol will be collected monthly by research staff and reviewed monthly by the PI/Project Managers. Adherence of participants will be evaluated by the Project Managers. If adherence falls below the expected rate, which might inhibit the ability of the study to test its primary hypotheses, the Project Managers will suggest a conference call for study investigators to discuss methods for improving adherence.

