Research Hypotheses for Secondary Aim 1: Participants in the PPMI condition will have greater retention on buprenorphine treatment (i.e., lower treatment dropout) over the entire 12-months of follow-up. The primary goals for the project are to test the preliminary efficacy of an 8-session Psychosocial Pain Management Intervention (PPMI), as compared to an EUC control condition, on retention on buprenorphine treatment. We will evaluate measures of self-reported information gained from the TLFB on buprenorphine treatment use on a daily basis and data collected from weekly surveys completed by the participant. For those with multiple sources of information available (TLFB and self-report survey), we will use the comparison between sources of data to develop reasonable assumptions about actual consumption. It is anticipated that individuals will occasionally miss a day of buprenorphine treatment without having dropped out of treatment. Discontinuation of treatment will be operationalized as 7 days in a row without taking buprenorphine. Analysis will follow a time-to-event (survival analysis) framework where the outcome is time until discontinuing buprenorphine treatment.

We will first descriptively calculate the percent still receiving buprenorphine at the 6-, 9-, and 12-month follow-ups. The independent variable of interest is an indicator of group (PPMI vs. EUC). Analysis will use an intent-to-treat framework, where participants are classified by the condition they were randomized to, regardless of what they received. Cox Proportional Hazards regression models will be used to test the association between group assignment and time to dropping out of buprenorphine treatment at 12-months. We will test if assumptions for this modeling technique are met, and if they are not, consider including a covariate*time interaction or stratification in Cox modeling, or variable transformations or alternative modeling strategies, if necessary.

Research Hypotheses for Secondary Aims 2 and 3: Compared with participants randomized to the EUC (control) condition, participants randomized to the PPMI condition will report a greater reduction in pain level, an increase in pain-related functioning, and a decrease in frequency of substance use at: (1) 3-months; and (2) 12-months post-intervention. We will calculate the

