means and standard deviations for these outcomes at baseline, 1-, 3-, 6-, 9-, and 12-months, as well as change scores from baseline for the two groups. We hypothesize that participants randomized to the PPMI will have less pain, better functioning, and lower frequency of opioid use at follow-ups compared to EUC. These secondary outcomes are hypothesized to meet the assumptions of continuous variables, and we will consequently use t-tests to make comparisons. If, however, the distribution of a given outcome measure is skewed, alternative modeling strategies will be used. We will use a linear mixed-effects model and estimate the treatment effect as the difference in the time-averaged changes from baseline in pain levels (using the NRS-I) and in pain-related functioning (using the BPI) over the course of follow-up (namely, at 3-months for secondary aim 2 and at 12-months for secondary aim 3). Because reduction in pain is of key interest, the analysis will model change-scores from baseline in the response variable as the dependent variable, and the independent variables will include the baseline values of the response variable, time in months since randomization and the treatment group indicator. The parameter estimate of the treatment group indicator will estimate the time-averaged treatment effect. If the graphical exploration (described above) shows potentially differential linear decrease in pain over time, we will include an interaction of time by treatment group indicator to model and test for this. For frequency of substance use, we will first assess the distribution of measures collected to assess alcohol use, illicit drug use and prescription opioid medication use to determine whether a summary or composite measure of each of these may represent the use or misuse more appropriately. For example, illicit drug use will be obtained as the number of days the participant used each of multiple drugs, and thus we may consider combining the days of any of the illicit drug use. We will also combine the alcohol and drug use data obtained using TLFB interviews as the percent days abstinent from alcohol and drugs during the past 30 days at each assessment time. We will then check the distribution of the substance use and prescription medication misuse (measured using the TLFB), and unless the data are highly skewed, we will use a linear mixed-effect model to test the hypothesis and to estimate the treatment effect as the difference in the time-averaged changes from baseline in these outcome measures over the course of the 12-month follow-up period.

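### The Cox and mixed models do not name the three randomisation stratification factors, and section 5.1 leaves adjustment for follow-up treatment data open

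*Combined protocol and SAP*

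**What the plan says.** **Randomisation.** Sections 3, 4.3, 6.2.2 and 9.2.1 stratify by sex assigned at birth, past-year heroin use and veteran status, which gives 8 strata. Section 9.2.1 adds: "There is no sample size goal for each stratum". Section 4.3 gives a prognostic reason for two of the factors: "trajectories of treatment retention and outcomes varies between men and women, as well as between those with history of heroin use". It makes no such claim for veteran status.

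**Retention models.** The primary Cox regression in 9.6 is to "test the association between group assignment and time to dropping out of buprenorphine treatment at 3-months", and the secondary one tests "the association between group assignment and time to dropping out of buprenorphine treatment at 12-months". Group is the only variable named in either, and in the Cox model of 9.3. Stratifying the Cox model is mentioned only as one remedy to consider if model assumptions fail, with no stratifying variable given.

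**Mixed models.** For pain and pain-related functioning, 9.6 says "the independent variables will include the baseline values of the response variable, time in months since randomization and the treatment group indicator". A time-by-group interaction may be added. The substance-use mixed model has no covariate list.

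**Confounders.** Under Treatment as Usual, 5.1 says treatment experiences will be recorded at baseline and "at all follow-up assessments in order to control for any potential confounding factors during analyses". It names no variable and no model. By contrast, 9.6 labels adjustment for session attendance, which is also measured after randomisation, as exploratory.

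**The concern.** There are two separate gaps.

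1. **Stratification factors.** Stratified allocation balances the arms on these factors. If the factors predict dropout, a group-only analysis ignores that balance: its standard error is too large for the design and the test becomes conservative. The cost is some power; there is no false-positive risk. The plan does not say which analysis it intends, so the primary covariate set is undecided.

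2. **Follow-up treatment data.** Treatment use recorded after randomisation can be affected by arm, or can follow from staying in or leaving buprenorphine treatment. Section 5.3.1 makes the second route concrete: a provider may require counselling or self-help attendance for the patient to stay on buprenorphine. Conditioning on such a variable in a confirmatory model would distort the randomised comparison. Section 5.1 does not rule this out.

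**Working it through.** **Step 1. Reproduce the plan's power.** Section 9.2 assumes 50% dropout in EUC, a hazard ratio (HR) of 0.5 and two-sided alpha of 0.05, which "would achieve >85% power with a sample size of 200, or 100 per group".

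- PPMI event probability: 1 − 0.5^0.5 = 0.293
- Events: 100 × 0.50 + 100 × 0.293 = 79.3
- Schoenfeld: Φ(√(79.3 × 0.25) × ln 2 − 1.96) = Φ(3.086 − 1.960) = Φ(1.126) = 87.0%

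The stated power reproduces with no covariates, so the sample size is not in dispute.

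**Step 2. Effect of omitting the factors from the Cox model.** This was simulated with N = 200, 1:1 permuted blocks of 2, 4 or 6 within 8 strata, 50% EUC events by 3 months and a conditional HR of 0.5. Section 4 expects that "approximately 41% of the sample will be female in the community population and 10% of the veteran sample will be female". The assumptions not in the documents are 25% veterans, 50% heroin use, equal prognostic HRs for sex and heroin use, and no veteran effect. There were 24,000 runs per scenario, so the simulation error on power is about √(0.86 × 0.14 / 24,000) = 0.2 points.

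| Factor HR (assumed) | Power, group only | Power, three main effects | Type I error, group only |
|---|---|---|---|
| 1.2 | 86.1% | 86.6% | 4.8% |
| 1.5 | 85.3% | 86.5% | 4.4% |
| 2.0 | 83.6% | 86.8% | 3.8% |
| 2.5 | 81.3% | 87.3% | 3.2% |

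Adjusted type I error was 5.1 to 5.2%. At factor HR 2.0 the mean estimated HR was 0.516 unadjusted and 0.493 adjusted, with model standard errors of 0.232 and 0.233. Adjustment therefore does not narrow the interval, and part of the HR difference is only marginal versus conditional.

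Varying veterans over 10 to 50% and heroin use over 30 to 70% gave gains of 0.3 to 0.5 points (HR 1.2), 1.0 to 1.3 (HR 1.5) and 2.7 to 3.3 (HR 2.0).

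A separate simulation made all three factors prognostic (1,500 trials per cell). Unadjusted versus adjusted power was 84 versus 85% at factor HR 1.5, 82 versus 86% at 2.0 and 78 versus 88% at 3.0. An 8-stratum Cox model gave 84, 84 and 87%.

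**Step 3. Mixed models.** If the strata explain a share R² of the variance, unadjusted type I error is 2 × (1 − Φ(1.96/√(1 − R²))). For assumed R² of 2, 5 and 10% this gives 4.8, 4.4 and 3.9%. Because these models already adjust for the baseline response, R² should be read as variance left after that.

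**Step 4. Adjusting the Cox model for a follow-up treatment indicator.** Here the indicator depends on retention, with assumed percentages and 10,000 runs each.

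| Indicator present: retained / dropped out | HR, without to with | Power, without to with |
|---|---|---|
| Unrelated to arm and outcome | 0.49 both ways | 86.3% to 86.4% |
| 50% / 30% | 0.496 to 0.503 | 86.8% to 84.9% |
| 60% / 20% | 0.496 to 0.528 | 85.6% to 78.1% |
| 70% / 10% | 0.497 to 0.573 | 86.0% to 66.5% |

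Under no treatment effect, the 60/20 case rejected 5.1% of the time.

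Dependence on arm was run separately, with the indicator raised from 30% to 60% by PPMI. Adjustment moved the HR from 0.51 to 0.59 when 25% of the log hazard ratio passed through the indicator, and from 0.52 to 0.70 when 50% did. Those shares are assumptions.

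**Step 5. Why not 8 strata in the model.** At 10% female, an assumed 20 to 100 veterans gives 2 to 10 veteran women, split over two heroin-use cells.

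**The case against.** - **The omission is not an error.** An unadjusted Cox test is valid and matches the covariate-free power calculation. At factor HRs of 1.2 and 1.5 the loss is 0.5 and 1.2 points, and unadjusted power still meets the stated 85%. Larger losses need effect sizes that the documents do not supply. All of this stands and limits the weight of the first gap.

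- **The two gaps pull against each other.** If the term lists in 9.6 are complete, no follow-up variable enters; if they are not, omission of the strata is not proven. This is fair. However, both readings leave the covariate set unstated, although 9.1 says the main analyses will be planned in advance.

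- **Section 5.1 describes data collection.** Section 9.1 separates confirmatory from exploratory analyses, and 9.6 applies that to session attendance. These passages point away from adjustment for follow-up data, so the second gap is unclear wording and not a planned post-randomisation adjustment. They do not expressly exclude the 5.1 data.

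- **The t-test sentences.** Sections 9.5.1 and 9.6 also mention t-tests for the secondary outcomes, and these cannot carry covariates. That is correct; the proposed change concerns the Cox and mixed models only.

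**Conclusion.** The concern holds on both counts, at moderate weight: a change that should be made, not one on which the trial's validity depends.

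No stated Cox or mixed model names the stratification factors. Omitting them costs about 0.5 to 6 points of power when sex and heroin use each have a dropout HR of 1.2 to 2.5. It takes power below the plan's 85% at HR 2.0 and above, and it never inflates type I error. These figures rest on assumed prognostic effects, veteran share and heroin-use share.

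The 5.1 wording is a conditional risk. It does no harm if the follow-up variable is unrelated to arm and outcome. If the variable tracks retention, the HR moves to between 0.50 and 0.57 and power falls to between 85% and 67%, under assumed associations of which 70/10 is a deliberate extreme.

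**What to change.** - **Section 9.6, Cox models:** state that sex, past-year heroin use and veteran status enter the 3- and 12-month models as main effects, not as 8 strata. Note that the adjusted HR is a conditional estimate, and report the unadjusted HR beside it.
- **Section 9.6, mixed models:** add the same three main effects to the models for pain, functioning and substance use.
- **Section 5.1:** state that confirmatory models adjust only for baseline variables, and that follow-up treatment use is reported descriptively or in labelled exploratory analyses.
- **Optional:** prespecify baseline time on buprenorphine as a further covariate.

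The cost is a few sentences in 9.6 and 5.1. All three factors are already recorded for randomisation, so no new data, participants or procedures are needed.
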